10.4.4. Safety Analysis

For the double-blind period, summaries of safety results will be presented by treatment group for patients in the double-blind SAF. Summaries of safety results for the open-label period will be presented for patients in the open-label SAF, by the total patients administered open-label study treatment (total), as well as by the patient subgroups of study treatment received in the DBTP (ie, evinacumab, placebo). No formal inferential testing will be performed. Summaries will be descriptive in nature.

All safety analyses will be performed using the following common rule:

- The baseline value is defined as the last available value before the first dose of double-blind study treatment.

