4.8. Safety Variables

Patient safety will be assessed through the collection of reported adverse events (AEs), clinical laboratory data, vital signs, and ECG. Unless otherwise noted, the baseline value is defined as the last available value before the first dose of double-blind study treatment.

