4.8.1. Adverse Events Variables

The period of safety observation starts from the time when the patient gives informed consent and continues into the following periods:

- The PRE-TREATMENT period is defined from the day the ICF is signed to the day before the first dose of double-blind study treatment administration.
- The double-blind treatment-emergent adverse event (TEAE) period is defined from the day of the first dose of double-blind study treatment administration to the day of the last dose of double-blind study treatment administration + 168 days (24 weeks) for those patients not proceeding into the OLTP, or up to the day before the first dose of open-label study treatment administration for those patients proceeding into the OLTP

The double-blind TEAE period will include:

- The TREATMENT period is defined from the day of first double-blind study treatment administration up to the day of last double-blind study treatment administration + 35 days. For patients entering into the OLTP, the treatment period will be truncated at the day before the first dose of open-label study treatment administration.
- The RESIDUAL TREATMENT period is defined from the day of last double-blind study treatment administration + 36 days up to the day of last double-blind study treatment administration + 168 days (24 weeks), or up to the day before first dose of open label study treatment administration, whichever is earlier.
- The open-label treatment-emergent adverse event (TEAE) period is defined from the day of the first open-label study treatment administration to the day of the last open-label study treatment administration + 168 days (24 weeks). For patients entering the open-label study R1500-CL-1719, the TEAE period will be truncated at the day before first study treatment administration in R1500-CL-1719.

The open-label TEAE period will include:

- The TREATMENT period is defined from the day of first open-label study treatment administration up to the day of last open-label study treatment administration + 35 days.
- The RESIDUAL TREATMENT period is defined from the day of last open-label study treatment administration + 36 days up to the day of last open-label study treatment administration + 168 days (24 weeks).

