5.8. Analysis of Safety Data

The summary of safety results will be presented separately for the DBTP and OLTP, unless otherwise noted. Safety summaries for the DBTP will be presented by treatment groups (evinacumab, placebo) containing patients from the double-blind safety analysis set. Safety summaries for the OLTP will be presented by all patients and by treatment group in DBTP (i.e.,

evinacumab, placebo), for patients in the open-label safety analysis set. No formal inferential testing will be performed for either period. Summaries will be descriptive in nature.

General common rules

All safety analyses will be performed, unless otherwise specified, using the following common rules:

- Safety data in patients who do not belong to the safety analysis set (i.e., exposed but not randomized) will be listed separately.
- PCSV values are defined as abnormal values considered medically important by the Sponsor according to predefined criteria/thresholds based on literature review and defined by the Sponsor for clinical laboratory tests and vital signs (PCSV version dated January 2009 [Appendix 10.4]). Considering that the threshold defined in the PCSV list for monocytes and basophils can be below the ULN, the following PCSV criterion will be used for the PCSV analysis of monocytes and basophils:
 - PCSV criterion for monocytes: >0.7 Giga/L or $>ULN$ (if $ULN \geq 0.7$ Giga/L).
 - PCSV criterion for basophils: >0.1 Giga/L or $>ULN$ (if $ULN \geq 0.1$ Giga/L).
- PCSV criteria will determine which patients had at least 1 PCSV during the respective TEAE periods, taking into account all evaluations including unscheduled or repeated evaluations.
- The treatment-emergent PCSV denominator by treatment group for a given parameter will be based on the number of patients assessed for that given parameter at least once during the respective TEAE periods.
- All measurements, scheduled or unscheduled, fasting or not fasting, will be assigned to Global Analysis Windows defined in Appendix 10.2 /Table 1 in order to provide an assessment for the screening visit through follow-up visit time points.
- For quantitative safety parameters including central laboratory measurements and vital sign scores, descriptive statistics will be used to summarize observed values and change from baseline values by visit.

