6.1. Definition of Baseline for Efficacy/Safety Variables

Unless otherwise specified, the baseline assessment is programmatically as the last available measurement prior to the date of the first double-blind study treatment administration. For patients randomized and not treated, the baseline value is defined as the last available value prior to the date of randomization.

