10.4. Criteria for Potentially Clinically Significant Values (PCSV)

Parameter	PCSV
Clinical chemistry	
ALT	By distribution analysis: >2 ULN and baseline \leq 2 ULN >3 ULN and baseline \leq 3 ULN >5 ULN and baseline \leq 5 ULN >10 ULN and baseline \leq 10 ULN >20 ULN and baseline \leq 20 ULN
AST	By distribution analysis: >2 ULN and baseline \leq 2 ULN >3 ULN and baseline \leq 3 ULN >5 ULN and baseline \leq 5 ULN >10 ULN and baseline \leq 10 ULN >20 ULN and baseline \leq 20 ULN
Alkaline Phosphatase	> 1.5 ULN and baseline \leq 1.5 ULN
Total Bilirubin	> 1.5 ULN and baseline \leq 1.5 ULN > 2 ULN and baseline \leq 2 ULN
Conjugated bilirubin	> 35% total bilirubin (when total bilirubin >1.5 ULN)
ALT and Total Bilirubin	ALT > 3 ULN and Total Bilirubin > 2 ULN and baseline ALT \leq 3 ULN or Total bilirubin \leq 2 ULN
CPK	> 3 ULN and \leq 5 ULN and baseline \leq 3ULN >5 ULN and \leq 10 ULN and baseline \leq 5 ULN >10 ULN and baseline \leq 10 ULN
Creatinine	\geq 150 μ mol/L (adults) \geq 30% from baseline \geq 100% from baseline
CLcr (mL/min) (Estimated creatinine clearance based on the Cockcroft-Gault equation)	\geq 15 - <30 (severe decrease in GFR) \geq 30 - < 60 (moderate decrease in GFR) \geq 60 - <90 (mild decrease in GFR) \geq 90 (normal GFR)
eGFR (mL/min/1.73m ²) (Estimate of GFR based on an MDRD equation)	\geq 15 - <30 (severe decrease in GFR) \geq 30 - < 60 (moderate decrease in GFR) \geq 60 - <90 (mild decrease in GFR) \geq 90 (normal GFR)

Parameter	PCSV
Uric Acid Hyperuricemia: Hypouricemia:	>408 µmol/L <120 µmol/L
Blood Urea Nitrogen	≥17 mmol/L
Chloride	<80 mmol/L >115 mmol/L
Sodium	≤129 mmol/L ≥ 160 mmol/L
Potassium	< 3 mmol/L ≥ 5.5 mmol/L
Glucose Hypoglycaemia Hyperglycaemia	≤ 3.9 mmol/L and < LLN ≥ 7 mmol/L (fasted); ≥ 11.1 mmol/L (unfasted)
HbA1c	>8%
Albumin	≤25 g/L
Hs-CRP	> 2 ULN or >10 mg/L, if ULN not provided
Hematology	
WBC	< 3.0 Giga/L (3000/ mm ³) (Non-Black) < 2.0 Giga/L (2000/ mm ³) (Black) ≥16.0 Giga/L (16000/ mm ³)
Lymphocytes	>4.0 Giga/L
Neutrophils	< 1.5 Giga/L (1500/ mm ³) (Non-Black) < 1.0 Giga/L (1000/ mm ³) (Black)
Monocytes	>0.7 Giga/L
Eosinophils	> 0.5 Giga/L (500/ mm ³) or > ULN if ULN ≥ 0.5 Giga/L
Hemoglobin	≤115 g/L (Male); ≤95 g/L (Female) ≥185 g/L (Male); ≥165 g/L (Female) Decrease from Baseline ≥15 g/L Decrease from Baseline ≥20 g/L
Hematocrit	≤0.37 v/v (Male) ; ≤0.32 v/v (Female) ≥0.55 v/v (Male) ; ≥0.5 v/v (Female)
RBC	≥6 Tera/L

Parameter	PCSV
Platelets	< 100 Giga/L (100 000/mm ³) ≥700 Giga/L (700000/mm ³)
Urinalysis	

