pH	≤4.6 ≥8
Vital signs	
HR	≤ 50 bpm and decrease from baseline ≥ 20 bpm ≥ 120 bpm and increase from baseline ≥ 20 bpm
SBP	≤ 95 mmHg and decrease from baseline ≥ 20 mmHg ≥ 160 mmHg and increase from baseline ≥ 20 mmHg
DBP	Young and elderly patients ≤ 45 mmHg and decrease from baseline ≥ 10 mmHg ≥ 110 mmHg and increase from baseline ≥ 10 mmHg
Orthostatic Hypotension	SBP St – Su ≤ - 20 mmHg DBP St – Su ≤ - 10 mmHg
Weight	≥5% increase versus baseline ≥5% decrease versus baseline
ECG parameters	
HR	≤ 50 bpm and decrease from baseline ≥ 20 bpm ≥ 120 bpm and increase from baseline ≥ 20 bpm
PR	≥220 ms and increase from baseline ≥20 ms
QRS	≥ 120 ms
QTc Borderline Prolonged* Additional	Absolute values (ms) Borderline 431-450 ms (Male) 451-470 ms (Female) Prolonged* > 450 ms (Male) > 470 ms (Female) QTc ≥500 ms Increase versus baseline (Males and Females) Borderline Δ 30-60 ms Prolonged * Δ > 60 ms

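### One pre-placebo safety baseline and a date-based period boundary put abnormalities that arose on placebo into the open-label laboratory, vital-sign and ECG counts of ex-placebo patients

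*SAP*

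**What the plan says.** The safety baseline is fixed once for the whole study. SAP 4.8 reads: "Unless otherwise noted, the baseline value is defined as the last available value before the first dose of double-blind study treatment". SAP 6.1 repeats it as "the last available measurement prior to the date of the first double-blind study treatment administration". Protocol 10.4.4, the same in both protocol versions, introduces the rule with "All safety analyses will be performed using the following common rule" and then states: "The baseline value is defined as the last available value before the first dose of double-blind study treatment". The qualifier that opens the SAP 4.8 sentence is never taken up to define an open-label baseline for laboratory, vital-sign or ECG data. The list of departures from the protocol in SAP 1.2.4 does not mention baseline.

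On counting, SAP 5.8 says: "PCSV criteria will determine which patients had at least 1 PCSV during the respective TEAE periods". SAP 5.8.3 and 5.8.4 then split the PCSVs by whether baseline was normal or missing, or abnormal, and SAP 5.8.5 does the same for abnormal ECGs. Several criteria in SAP 10.4 are defined against baseline, for example weight ("≥5% increase versus baseline") and haemoglobin ("Decrease from Baseline ≥15 g/L"). Open-label tables show all patients together and by former arm (SAP 5.8).

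On periods, SAP 4.8.1 says: "The open-label treatment-emergent adverse event (TEAE) period is defined from the day of the first open-label study treatment administration". For patients who continue, the double-blind period stops the day before. Footnote 14 to the treatment-period schedule in SAP 10.9 has the week-24 assessments and blood samples done before that dose.

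**The concern.** For a patient on evinacumab throughout, the value before the first double-blind dose is the pre-drug reference. For an ex-placebo patient it is not: 24 weeks on placebo lie between that value and the first evinacumab infusion. Read against the early baseline, a laboratory change that developed on placebo and persists looks like one that began in the evinacumab period from a normal start.

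The adverse-event rules avoid this. SAP 4.8.1.1 requires an open-label event to develop, worsen or become serious within the open-label period. PCSVs face no such test, although SAP 5.8 calls their denominator treatment-emergent. The same abnormality in the same patient can thus be non-emergent as an adverse event and counted as a laboratory value.

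Safety and tolerability is a secondary objective (SAP 1.2.2), and the ex-placebo column is where a reader would look for what appears after starting the drug.

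**Working it through.** 1. **Patients exposed.** SAP 2.2 plans 57 patients (38 and 19) for a difference of 38 points, SD 35, two-sided 0.05 and 90% power, with 5% non-evaluable and 15% dropout. This reproduces. Two-sample t-test power is 0.899 at 14:28 and 0.919 at 15:30, so 45 evaluable patients are needed. Then 45/(1 − 0.20) = 56.25, or 45/(0.95 × 0.85) = 55.7, and the next 2:1 total is 57. At most 19 placebo patients can cross over; 19 × 0.85 = 16.15, so about 16 after planned dropout.

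2. **Effect of the baseline, one patient (assumed values).** A placebo patient has ALT 1.0 × ULN before double-blind dosing, 3.4 at week 24 pre-dose and 3.5 at week 32. SAP 10.4 has a band for above 3 × ULN with baseline at or below 3 × ULN.
   - SAP baseline 1.0: the week-32 value meets the band and is an open-label PCSV.
   - Last value before open-label dosing, 3.4: it does not.

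3. **Effect of the boundary.** The week-24 value of 3.4 is drawn before any evinacumab, but on the first open-label dosing day. By SAP 4.8.1 that day lies in the open-label period and outside the double-blind one. The value is therefore counted as open-label even if it has resolved by week 32. Protocol 10.4.4.2 and the windows in SAP 10.2 place it correctly at week 24 for by-visit tables, but PCSV and ECG counts follow the treatment-emergent periods. ECG shows this most sharply: the only scheduled post-baseline ECGs up to week 48 are at weeks 24 and 48. Read literally, a continuing patient has no scheduled ECG in the double-blind count.

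4. **Which results move.**
   - Criteria that refer to baseline (ALT, AST, alkaline phosphatase, bilirubin, CPK, creatinine percentage change, haemoglobin fall, weight): the count itself can change.
   - Heart rate and blood pressure: the count can change, but an absolute threshold must also be met.
   - Threshold-only criteria (such as sodium, potassium, albumin, platelets): only the baseline-category split changes, apart from pre-dose week-24 values.
   - Adverse events: no change.

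5. **Size.** One carried-over case adds 1/19 = 5.3 to 1/16 = 6.3 percentage points to the ex-placebo column. In the pooled column (57 × 0.85 = 48.45, about 48) it adds 1/57 = 1.8 to 1/48 = 2.1 points. Neither document gives a background rate, so the share p of ex-placebo patients with a carried-over abnormality on a given parameter is assumed, with patients independent:

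| p (assumed) | Expected cases, 19p | Chance of at least one, 1 − (1 − p)^19 |
|---|---|---|
| 2% | 0.38 | 32% |
| 5% | 0.95 | 62% |
| 10% | 1.9 | 86% |
| 20% | 3.8 | 99% |

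With 16 patients the chances are 28%, 56%, 81% and 97%.

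**The case against.** The single baseline is a stated convention, applied consistently. SAP 4.7, 5.7 and 5.12 say explicitly that the double-blind baseline serves both periods for efficacy and quality of life. Safety is descriptive, with no formal testing. Open-label results are split by former arm, PCSVs are listed by patient, and week-24 values appear in the by-visit tables, so a careful reader can find carry-over among 16 to 19 patients. Many criteria are absolute, and the Hy's law listing does not use baseline. Haematology, chemistry and CPK are not drawn at week 28, so after dosing a laboratory abnormality must persist or recur to week 32.

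Most of this stands and limits the point. Two parts do not fully answer it. Listings and by-visit means let a reader undo the misplacement by hand, but the summary counts remain as they are. Persistence to week 32 is not needed while the boundary puts the week-24 value itself in the open-label count.

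A reader might infer that the plan attributes placebo abnormalities to evinacumab. The text does not go that far: it reports incidence within a period and draws no causal conclusion. A reader might also infer a bias of a definite size, such as 5 to 13 points from one or two cases per parameter, but that rests on an assumed number of cases. Nor should the baseline simply be replaced for ex-placebo patients. With the boundary unchanged, an abnormality seen only at week 24 would be counted in neither period. ALT rising from 3.1 to 4.9 × ULN on evinacumab would meet no band in SAP 10.4.

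**Conclusion.** The point holds in limited form. As written, the baseline and the period boundary together place placebo-period laboratory, vital-sign and ECG abnormalities in the open-label counts of ex-placebo patients, usually under normal baseline, and their open-label change from baseline includes 24 weeks of placebo drift. The misplacement reaches the ex-placebo and pooled open-label columns only. Separately, the boundary removes pre-dose week-24 values from the double-blind counts of continuing patients in both arms.

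The size is about 5 to 6 points per case in the ex-placebo column and about 2 in the pooled column, with an unknown number of cases. This assumes that the patient would not otherwise have met the criterion during the open-label period. Efficacy and adverse-event results are untouched. This is a worthwhile, inexpensive correction to descriptive safety tables.

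**What to change.** Make two changes, together:

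1. In SAP 4.8.1, 5.8 and 5.8.3 to 5.8.5, state that laboratory, vital-sign and ECG measurements taken before the first open-label dose on that day belong to the double-blind period for PCSV and ECG counts, in both former arms.
2. For ex-placebo patients in the open-label safety set, add tables of PCSVs, PCSVs by baseline category, ECG by baseline status and by-visit change that use the last value before the first open-label dose as baseline. Keep the tables on the double-blind baseline beside them, so that further worsening is not hidden. Keep the double-blind baseline for ex-evinacumab patients.

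The week-24 pre-dose chemistry, haematology, CPK, weight, vital signs and ECG are already scheduled, so no new data are needed. SAP Section 1 allows revision before the first-step lock, and SAP Section 7 already includes open-label safety in that step. The cost is some programming, a few extra tables, and a footnote explaining two baseline dates.

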4.8.1. Adverse Events Variables

The period of safety observation starts from the time when the patient gives informed consent and continues into the following periods:

- The PRE-TREATMENT period is defined from the day the ICF is signed to the day before the first dose of double-blind study treatment administration.
- The double-blind treatment-emergent adverse event (TEAE) period is defined from the day of the first dose of double-blind study treatment administration to the day of the last dose of double-blind study treatment administration + 168 days (24 weeks) for those patients not proceeding into the OLTP, or up to the day before the first dose of open-label study treatment administration for those patients proceeding into the OLTP

The double-blind TEAE period will include:

- The TREATMENT period is defined from the day of first double-blind study treatment administration up to the day of last double-blind study treatment administration + 35 days. For patients entering into the OLTP, the treatment period will be truncated at the day before the first dose of open-label study treatment administration.
- The RESIDUAL TREATMENT period is defined from the day of last double-blind study treatment administration + 36 days up to the day of last double-blind study treatment administration + 168 days (24 weeks), or up to the day before first dose of open label study treatment administration, whichever is earlier.
- The open-label treatment-emergent adverse event (TEAE) period is defined from the day of the first open-label study treatment administration to the day of the last open-label study treatment administration + 168 days (24 weeks). For patients entering the open-label study R1500-CL-1719, the TEAE period will be truncated at the day before first study treatment administration in R1500-CL-1719.

The open-label TEAE period will include:

- The TREATMENT period is defined from the day of first open-label study treatment administration up to the day of last open-label study treatment administration + 35 days.
- The RESIDUAL TREATMENT period is defined from the day of last open-label study treatment administration + 36 days up to the day of last open-label study treatment administration + 168 days (24 weeks).
- The POST-TREATMENT period is defined from the day after the end of the respective TEAE periods to the last study visit. For patients entering the open-label study R1500-CL-1719, the post-treatment period will be truncated at the day before first study treatment administration in R1500-CL-1719.

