10.4.4.2. Other Safety

Definitions

The following definitions will be applied to laboratory parameters and vital signs:

- The potentially clinically significant value (PCSV) criteria are defined as abnormal values considered medically important by the sponsor according to predefined criteria/thresholds based on literature review and defined by the sponsor for clinical laboratory tests and vital signs. PCSV criteria will be provided in the SAP.
- PCSV criteria will determine which patients had at least 1 PCSV during the respective TEAE periods (double-blind and open-label), taking into account all evaluations performed during the respective TEAE periods, including unscheduled or repeated evaluations. The number of all such patients will be the numerator for the PCSV percentage.
- Double-blind treatment period: The treatment period used for the quantitative analysis of laboratory and vital signs data in the double-blind period is defined from the day after the first dose of double blind study treatment to the day of the last dose of double-blind study treatment + 28 days for those patients not proceeding into the OLTP, or up to the day of the first dose of open-label study treatment administration for those patients proceeding into the OLTP.
- Open-label treatment period: The treatment period used for quantitative analysis of laboratory and vital signs data in the open-label study period is defined from the day after the first dose of open-label study treatment to the day of the last dose of open-label study treatment + 28 days.

Analysis

Summary statistics of all laboratory variables (including lipid HDL-C) and all vital signs parameters (raw data and changes from baseline) will be calculated for each protocol scheduled visit assessed during the respective treatment periods. For selected parameters, mean changes from

baseline with the corresponding SE may be plotted over time (at same time points) in each treatment group.

The incidence of PCSVs at any time during the respective TEAE periods will be summarized regardless of the baseline level, and again according to the following baseline categories:

- Normal/missing
- Abnormal according to PCSV criterion or criteria

For laboratory parameters for which a PCSV criterion is not defined, similar table(s) using the normal range will be provided, regardless of baseline level.

Listings will be provided with flags indicating the laboratory values meeting PCSV criteria.

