2.3. Study Plan

This study consists of the following periods: up to an 8-week run-in period (for patients who may require HoFH genotyping, for patients whose background medical lipid modifying therapy (LMT) has not been stable prior to screening or whose apheresis settings and/or schedule have not been stable for at least 8 weeks prior to screening), a 2-week screening period, a 24-week double-blind treatment period (DBTP), and a 24-week open-label treatment period (OLTP), and a 24-week follow-up period after the last dose of study drug for those patients who choose not to enter the open-label study (See [Figure 1.](#))

The Study event table is presented in [Appendix 10.9](#).

Figure 1: Study Flow Diagram

Run-in ¹	Screening	Double-Blind Treatment ²	Open-Label Treatment ³	Follow-up ⁴
V1a Day -70	V1 Day -14	V2 Day 1 Baseline	V3 to V9 Wk 2 to 24	End of DBTP ³
			V10 to V15 Wk 28 to 48	End of OLTP
				V16 to V20 Wk 52 to 68 EOS

¹ Patients who are undergoing apheresis therapy with a schedule and/or apheresis settings that have not been stable for at least 8 weeks before the screening visit will enter a run-in period before the screening period. Patients who are on background LMT that has not been stable for at least 4 weeks (6 weeks for fibrates, 8 weeks for PCSK9 inhibitor antibodies) before the screening visit will enter the run-in period to stabilize their LMT before entering the screening period. Patients who have completed the R727-CL-1628 study and meet all the eligibility criteria for this study can be enrolled directly. The end of the open-label treatment visit from the R727-CL-1628 study can serve as the baseline/day 1 visit for this study.

² Patients will receive study drug IV Q4W starting at day 1.

³ The open-label treatment period begins at week 24 (day 169) when all patients will receive evinacumab 15 mg/kg IV Q4W. The last dose of evinacumab will be at week 44.

⁴ Follow-up only for patients who do not enter a separate, optional OL study, R1500-CL-1719 or prematurely discontinue study treatment in this study.

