10.2. Windows for Analysis Time Points

Below are the definitions for the visit windows programmatically imposed on measures repeatedly collected over the course of the study. These visit windows reflect the study schedule of assessments as described in the protocol.

The visit windows are constructed using ranges applied to the number of days in study (study days) when the measure is collected. Below are the relevant definitions for the analysis visit windows:

1. Study day is defined as the number of days since the first study treatment administration +1. The first study treatment occurs on
2. Study Day 1.
3. Open-label study day is defined as the number of days since the first open-label study treatment administration+1
4. Since the protocol specifies that measurements be collected before study treatment is administered on a given day, it is appropriate that baseline include Day 1.
5. For randomized but not treated patients, Day 1 is the day of randomization.

Table 1: Global Analysis Windows

Visit label	Targeted Study Day	Targeted Open-Label Study Day	Analysis Window in Study Day
Screening	< Day 1	N/A	Measurement obtained prior to first study treatment, and not defined as baseline visit
Baseline	1	N/A	Measurement obtained closest to first study treatment, while remaining prior to first study treatment
Week 2	15	N/A	2 to 21
Week 4	29	N/A	22 to 42
Week 8	57	N/A	43 to 70
Week 12	85	N/A	71 to 98
Week 16	113	N/A	99 to 126
Week 20	141	N/A	127 to 154
Week 24	169	Day 1	155 to 182 for patients not entering OLTP or 155 to first OL treatment day for patients entering OLTP
Week 28	197	29	first OL treatment day+1 to 210
Week 32	225	57	211 to 238
Week 36	253	85	239 to 266
Week 40	281	113	267 to 294
Week 44	309	141	295 to 322
Week 48	337	169	323 to 350
FU – W4	For patients prematurely discontinued trt: last study trt to 28 days after last study trt For patients completed OLTP: 365	For patients prematurely discontinued trt: last study trt to 28 days after last study trt For patients completed OLTP: 197	For patients prematurely discontinued trt: Last study trt day +1 to 56 days after last study trt For patients completed OLTP: 351 to 392

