2. Study assessments will be performed and blood samples will be collected before the dose of study drug in all patients. For patients undergoing apheresis: Study assessments will be performed and blood samples will be collected immediately before the lipid-apheresis procedure; study drug will be administered after the apheresis procedure. The timing between the baseline sample collection relative to the most recently completed LDL apheresis procedure, administration of a PCSK9 inhibitor or mipomersen should match the timing of the week 24 sample collection relative to the most recently completed LDL apheresis procedure, administration of a PCSK9 inhibitor or mipomersen. Depending on the duration between the LDL apheresis procedure and sample collection, the visit window may not apply.
3. Fasting sample will be collected for the lipid panel: total-C, calculated LDL-C, HDL-C, TG, non-HDL-C
4. Fasting sample will be collected for specialty lipid panel: Apo B, Apo A-1, and Lp(a)
5. On dosing days, vital signs should be recorded prior to IV infusion, and 30 minutes and 60 minutes post-IV infusion
6. ECG should be performed before blood samples are collected at visits requiring blood draws.
7. Assessment of Tanner Stage and sex hormones (includes luteinizing hormone, follicle stimulating hormone, estradiol, total testosterone) only applicable to patients <18 years old.
8. All laboratory samples should be collected before administration of study drug.
9. WOCBP only, confirm required contraception use and reminder pregnancy reporting
10. The ADA sample should be drawn before study drug administration
11. For patients who are not undergoing apheresis, the PK sample should be drawn before the dose of study drug and at the end of the infusion. For patients undergoing apheresis, a PK sample should be collected immediately before the apheresis procedure and a PK sample should be collected immediately after the apheresis procedure, prior to administration of study drug, and, again at the end of the infusion of study drug.
12. Including assay of total ANGPTL3.
13. Should be collected at the baseline visit, or at any study visit
14. All end of treatment (EOT) assessments will be performed and blood samples will be collected before the dose of open-label study drug in all patients. For patients undergoing

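### SAP 4.8.1 counts pre-dose week-24 measurements as open-label, so a patient dosed to plan has no scheduled post-baseline ECG or hs-CRP in the double-blind TEAE period

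*SAP*

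**What the plan says.** SAP 4.8.1 sets the TEAE periods by calendar day. For patients continuing into the OLTP, the double-blind period runs "or up to the day before the first dose of open-label study treatment administration for those patients proceeding into the OLTP". The next definition begins: "The open-label treatment-emergent adverse event (TEAE) period is defined from the day of the first open-label study treatment administration". Neither separates pre-dose from post-dose on that day. Protocol 10.4.4.1 draws the same boundary.

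On the planned schedule, dosing and assessment share a day. SAP 2.3 states: "The open-label treatment period begins at week 24 (day 169) when all patients will receive evinacumab 15 mg/kg IV Q4W". Footnote 14 to the treatment-period schedule in SAP 10.9 puts the end-of-double-blind assessments ahead of that dose, and adds that "blood samples will be collected before the dose of open-label study drug in all patients".

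Two other passages treat the day differently. SAP 10.2, Table 1, gives the Week 24 window as "155 to 182 for patients not entering OLTP or 155 to first OL treatment day for patients entering OLTP", and its Week 28 window opens the day after. Protocol 10.4.4.2 defines a double-blind period that extends "or up to the day of the first dose of open-label study treatment administration for those patients proceeding into the OLTP", but only for quantitative summaries of laboratory and vital-sign data. Item 4 of SAP 10.2 supplies the reasoning for a pre-dose convention ("measurements be collected before study treatment is administered on a given day, it is appropriate that baseline include Day 1") and applies it only to baseline.

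**The concern.** The week-24 visit closes the randomised comparison. Its measurements reflect 24 weeks of double-blind treatment and are taken before any open-label drug. A rule that hands the whole day to the open-label period moves them to the wrong side of the boundary in every analysis counted by TEAE period:

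- abnormal ECGs (SAP 5.8.5)
- laboratory PCSVs and eDISH (SAP 5.8.3)
- vital-sign PCSVs (SAP 5.8.4)
- hs-CRP and HbA1c PCSVs (SAP 5.9)
- the HbA1c and fasting-glucose limbs of new-onset diabetes (SAP 10.3)

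Two things follow. The double-blind tables lose the last scheduled value, which for ECG and hs-CRP is the only post-baseline one. And a placebo patient who has never received evinacumab can contribute a week-24 abnormality to the open-label evinacumab tables.

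**Working it through.** The plan states no figure here, so the check is a count of scheduled assessments.

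**Inputs.** Target days from SAP 10.9: weeks 2, 4, 8, 12, 16, 20 and 24 are days 15, 29, 57, 85, 113, 141 and 169. Let D be the first open-label dosing day, 169 on plan.

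**Rules.** Under SAP 4.8.1 a post-baseline value on day d stays double-blind if d ≤ D − 1 = 168. If pre-dose values on day D are kept, it stays if d ≤ D = 169. For the laboratory panels, days 29, 57, 85, 113 and 169 against a limit of 168 leave 4 of 5.

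| Measurement | Scheduled post-baseline weeks to week 24 | Kept, SAP 4.8.1 | Kept, pre-dose rule |
|---|---|---|---|
| ECG | 24 | 0 of 1 | 1 of 1 |
| hs-CRP | 24 | 0 of 1 | 1 of 1 |
| HbA1c | 12, 24 | 1 of 2 | 2 of 2 |
| Haematology, chemistry, CPK, urinalysis | 4, 8, 12, 16, 24 | 4 of 5 | 5 of 5 |
| Weight | 4, 8, 12, 16, 20, 24 | 5 of 6 | 6 of 6 |
| Vital-sign visits (pre-infusion) | 2, 4, 8, 12, 16, 20, 24 | 6 of 7 | 7 of 7 |

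For vital signs only the pre-infusion week-24 reading is misplaced; the 30- and 60-minute readings do belong to the open-label period.

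**Sensitivity.** With assessments on day 169 and D = 170, the limit is 169 and nothing is lost. What matters is dosing on the assessment day, not day 169 itself.

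**Open-label side.** Through week 48, the scheduled values in the open-label TEAE period that precede its first dose are ECG 1 of 2 (weeks 24, 48), hs-CRP 1 of 2 (24, 48), HbA1c 1 of 3 (24, 36, 48) and laboratory panels 1 of 4 (24, 32, 40, 48).

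**New-onset diabetes, illustrations only.** SAP 10.3 needs two HbA1c values of at least 6.5%, or one if it is the last or the only value. Take day 1 as normal.

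- Week 12 high, week 24 normal: under SAP 4.8.1 week 12 becomes the last double-blind value, so the patient is a case. With week 24 kept, the patient is not.
- Week 12 normal, week 24 high: not a double-blind case under SAP 4.8.1; a case with week 24 kept.

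Both reversals also occur if day 1 is not counted, through the single-value default. For fasting glucose (two values of at least 126 mg/dL), status changes only when exactly one of weeks 4, 8, 12 and 16 is high and week 24 is high. The AE-term and medication limbs are separate.

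**By-visit summaries.** Table 1 still labels the day Week 24. However, SAP 5.9 confines its by-visit summaries of hs-CRP and HbA1c to the treatment period, and the period SAP 4.8.1 names TREATMENT is cut at the same day-before boundary. On that reading these summaries would lose the week-24 value too.

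**The case against.** The strongest reply is that the passages serve different purposes and need not agree. Table 1 assigns visit labels. Protocol 10.4.4.2 includes the dosing day only for quantitative summaries, and its own PCSV rule uses the TEAE periods. A reader might therefore infer that SAP 4.8.1 departs from the protocol; the documents do not support that, since protocol 10.4.4.1 has the same boundary. But the same distinction means Table 1 cannot repair the problem: SAP 5.8 states the TEAE-period PCSV rule and the window rule separately. The clock-time rule in SAP 6.4 selects among values on one day and does not assign a period.

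The second reply is that little is lost. Safety summaries are descriptive, values remain in listings and under the Week 24 label, and protocol text asks for clinically significant ECG abnormalities to be recorded as AEs. That stands as a limit on severity. It does not put the values in the right comparison, and an AE starting that day also falls in the open-label period.

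Third, same-day dosing may not be universal. Protocol 7.1 allows a dosing window of ±7 days, apheresis timing can override the visit window (footnote 2, SAP 10.9), and SAP 5.7.2.5 foresees long gaps between the two periods. This stands: same-day is the plan, not a documented frequency.

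A reader might also infer that a same-day patient stays in the hs-CRP PCSV denominator through the day-1 sample with nothing able to reach the numerator. SAP 5.8 counts patients assessed during the period, which includes day 1, but it calls this a treatment-emergent denominator, and a baseline sample may not qualify. On that other reading the patient leaves both counts. The text does not settle it.

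**Conclusion.** The point holds and should be fixed. Followed as written, SAP 4.8.1 leaves a patient first dosed open-label on the week-24 assessment day with no scheduled post-baseline ECG or hs-CRP value in the double-blind TEAE period, and with one value fewer for HbA1c, laboratory panels, weight and vital signs. It also counts pre-evinacumab abnormalities in placebo patients as open-label.

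The size is per patient. It assumes assessments and first open-label dose on one day, and no unscheduled values. The number of such patients is not given. Patients not entering the OLTP, or dosed on a later day than their assessments, lose nothing.

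It would go too far to say that all double-blind hs-CRP data are lost: the day-1 value stays in the period, and the 0 of 1 refers to post-baseline values. The diabetes patterns are not frequencies, and the effect on SAP 5.9 by-visit summaries depends on how its treatment period is read. Efficacy is unaffected. The R1500-CL-1719 truncation ("the TEAE period will be truncated at the day before first study treatment administration in R1500-CL-1719") uses similar wording, but the documents do not give the day of that first dose; it and the +28-day cut-off in SAP 5.8.3 and 5.8.4 are separate points.

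**What to change.** Add one rule to SAP 4.8.1 for measurement-based safety analyses: PCSV numerators and denominators, abnormal ECG, eDISH, the laboratory limbs of AESIs, and the treatment-period summaries in SAP 5.9. On the first open-label dosing day, values taken before the infusion belong to the double-blind period and later values to the open-label period.

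Also state that:

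- when a sample time is missing, scheduled laboratory samples and ECGs are taken as pre-dose, and vital signs follow their nominal pre- or post-infusion time point;
- PCSV numerators and denominators count post-baseline values only;
- reported AEs keep the day rule.

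List the change in SAP 1.2.4.

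The cost is SAP wording and one date/time condition in programming. SAP 6.3 says infusion date and time are already in the e-CRF, and no new data are needed. SAP 6.4 allows for missing measurement times, hence the defaults. One side effect needs a table footnote: a pre-dose week-24 abnormality may appear as a double-blind measurement and, if also reported as an AE, as an open-label event. The AE-term and medication limbs of new-onset diabetes can differ from the laboratory limbs in the same way.
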